2. PURPOSE

This single-center, clinical trial is being conducted over the course of 90 days [REDACTED]
[REDACTED] post-treatment visits in order to assess the efficacy and tolerability of the Sponsor's SkinPen device when used by men and women with [REDACTED]

3. HYPOTHESIS

The Sponsor's test materials will produce a statistically significant improvement in [REDACTED] appearance over the course of 90 days of use (4 monthly treatments), [REDACTED]

4. STUDY ENDPOINTS

4.1. Primary Endpoints

- Assessment of [REDACTED] wrinkles severity using a [REDACTED] Lemperle Wrinkle Assessment Scale [REDACTED] 3-month post-treatment.
- [REDACTED]
- Monitoring of adverse events throughout the course of the study.
- Subjects global aesthetic improvement assessment at [REDACTED]
[REDACTED]
- Patient Satisfaction Questionnaire [REDACTED]
- Measurements to assess skin thickness, skin density and firmness using the OCT, ultrasound and BTC 2000 respectively. [REDACTED]

5. TEST MATERIAL INFORMATION

5.2. Characterization and Stability

The Sponsor assumes responsibility for chemical characterization and stability of the study device(s).

5.3. Study Device Description(s)

5.4. Method of Treatment Assignment

Subjects will be numbered sequentially in the order in which they qualify for entry into the study. Prior to the start of the study, all subjects will receive treatment with the device as outlined in the instructions.

5.5. Study Device Accountability

Upon receipt of the clinical supplies at the site, designated study personnel will conduct a complete inventory of all study devices and assume responsibility for their storage and dispensation.

All supplies sent to the study site will be accounted for and in no case will be used [REDACTED]

[REDACTED] Used and unused devices will be returned to the Sponsor. Documentation will be provided for any devices not returned by subjects in the study file.

5.6. Storage of Study Devices

The Investigator will agree to keep all study devices in a safe and secure area with restricted access in accordance with applicable regulatory requirement(s).

5.7. Treatment Compliance

Any suspected non-compliance will be addressed by the Investigator or designee. The Investigator will make a determination if a subject's non-compliance will have an effect the outcome of the study and if the subject should be dropped from the study and/or data should be excluded from statistical analyses.

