6. SUBJECT ENROLLMENT AND INSTRUCTIONS

6.1. Number of Subjects

At least 33 subjects meeting the eligibility requirements are expected to complete participation in the clinical trial.

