10.4. Procedures for Reporting Adverse Events

At each visit, the Investigator or designee will question the subject about adverse events using an open question and taking care not to influence the subject's answer (e.g. "Have you noticed any change in your health since the last visit?").

[REDACTED]

[REDACTED]

[REDACTED]

[REDACTED]

[REDACTED]

[REDACTED]

The Sponsor will be notified of all AEs within 5 business days. Photographs will be taken to document any AEs if possible.

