11. ATTRITION

Clinical studies may experience attrition. Subjects will be made aware that they are free to withdraw from the study at any time for any reason, without prejudice. Otherwise, every effort will be made to have subjects complete the study as stated in this protocol, ensuring subject safety and following the provisions of the informed consent form.

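### Section 5.7 lets the Investigator remove a non-compliant subject from the study, with no visible provision for collecting Visit 6 and 7 outcomes or adverse events afterwards, and Section 11 is not reconciled with it

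*Combined protocol and SAP*

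**What the plan says.** Section 5.7 (Treatment Compliance) sets a condition and two remedies. The condition is a judgement: "The Investigator will make a determination if a subject's non-compliance will have an effect the outcome of the study". The remedies, available singly or together, are that the Investigator decides "if the subject should be dropped from the study and/or data should be excluded from statistical analyses". The legible text gives no objective criterion for choosing between them.

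Section 11 (Attrition) covers one route out of the study, the subject's own choice: "Subjects will be made aware that they are free to withdraw from the study at any time for any reason, without prejudice". It continues: "Otherwise, every effort will be made to have subjects complete the study as stated in this protocol". It does not mention removal by the Investigator.

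Sections 8.4 and 8.5 place wrinkle grading, the clinician and subject improvement ratings, the satisfaction questionnaire, imaging and the instrument measurements at Visits 6 and 7. Section 10.4 ties adverse event questioning to visits: "At each visit, the Investigator or designee will question the subject about adverse events". Section 4.1 lists adverse event monitoring and the skin measurements alongside the wrinkle assessment under primary endpoints. Section 6.1 plans on completers: "At least 33 subjects meeting the eligibility requirements are expected to complete participation in the clinical trial".

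**The concern.** Leaving data out of an analysis can be undone later, because the data exist. Removing a subject from the study may mean that they never exist. Section 5.7 offers both remedies under one judgement and does not say what follow-up, if any, continues after removal.

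This matters more here than in a controlled trial. Section 5.4 gives every subject the device, Section 15.2 tests change from baseline, and no comparator visible in the text would undergo the same selection. Subjects who comply poorly may be those who tolerated treatment poorly or saw little benefit. The judgement turns on the effect on the study outcome, and no legible text keeps it blind to response. Section 15.1 makes the per-protocol population primary, so an all-treated analysis is the natural check on it. That check, and a complete safety summary, need data from exactly the subjects who may be removed.

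**Working it through.** **Passages side by side**

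1. *Who can leave, and how.* Section 5.7: removal by the Investigator for non-compliance judged to matter. Section 11: withdrawal by the subject, otherwise best efforts at completion. Neither section refers to the other.
2. *What is due after treatment.* Sections 8.4 and 8.5 put the post-treatment outcomes at Visits 6 and 7. Section 4.1 refers to a wrinkle assessment 3 months after treatment.
3. *When removal could occur.* Section 8.4 lists the compliance review as step 2 and the outcome assessments as step 3. A removal decided at that review could therefore precede the Visit 6 assessments, and Visit 7 would still lie ahead. A removal decided after Visit 6 would put only Visit 7 at risk.
4. *What happens after removal.* The legible text neither provides for nor rules out a final visit, continued outcome visits or adverse event follow-up. Much of Sections 10.4 to 10.7 and 15.1 is redacted.

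**Size of the uncertainty (illustration)**

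The sample size reasoning in Section 6.1.1 is redacted, so the 33 completers cannot be reproduced. The plan gives no number of removals and no response rate. Assumptions: N = 33 treated subjects (borrowing the Section 6.1 figure, which counts completers), k of them removed without later data, and x of the other 33 − k improved, with x/(33 − k) close to 70%.

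- Rate among those retained = x/(33 − k)
- All-treated lower bound (no removed subject improved) = x/33
- All-treated upper bound (every removed subject improved) = (x + k)/33
- Width of the range = k/33

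| k | Retained | Lower bound | Upper bound | Width |
|---|---|---|---|---|
| 1 | 22/32 = 68.8% | 22/33 = 66.7% | 23/33 = 69.7% | 3.0 points |
| 3 | 21/30 = 70.0% | 21/33 = 63.6% | 24/33 = 72.7% | 9.1 points |
| 5 | 20/28 = 71.4% | 20/33 = 60.6% | 25/33 = 75.8% | 15.2 points |

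The retained rate lies inside the range each time, so the bias could run either way.

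**Power**

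For a one-sample two-sided t-test at alpha 0.05 (noncentral t) and an assumed standardized change of 0.5, power is 79.5% with 33 subjects, 78.2% with 32, 75.4% with 30 and 72.3% with 28. With few removals the loss of power is modest. The main issue is who is missing.

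**The case against.** The strongest reply is that no loss of data is stated. No passage says that collection ends on removal, and the sections most likely to cover follow-up are heavily redacted. That stands. A reader might infer that Visit 6 and 7 outcomes and later adverse events are never collected. The documents support only that no legible text provides for collecting them.

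A reader might also infer that Section 11 promises completion and flatly contradicts Section 5.7. It does not. It is a best-effort statement about completing the study under the protocol's own terms, and Section 5.7 is one of those terms. The two can be read together, but they need to be reconciled.

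Section 5.7 is also narrower than it may look. It requires a judgement that the non-compliance affects the outcome, and it allows data exclusion without removal. Small lapses need not lead to removal; sunscreen, for instance, is only recommended in Section 6.5.

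On safety, Section 10.9 describes expected reactions as settling within hours to days, and serious event reporting in Section 10.5 runs from notice to the Investigator rather than from a visit. No passage identifies a particular late reaction that would be missed. This limits the likely harm. It does not make the adverse event record complete, since routine questioning takes place at visits.

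Finally, retained subjects may still be excluded from the per-protocol analysis, so the primary estimate may not move. That is correct, and the case for the change does not depend on it.

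**Conclusion.** The point holds in a limited form and should be addressed. Section 5.7 permits removal from the study at the Investigator's discretion, the legible text gives no route for later outcomes or routine adverse event questioning, and Section 11 does not acknowledge this kind of removal. What is at stake is the ability to run an all-treated sensitivity analysis and to report adverse events completely.

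The size is unknown. Under the stated assumptions, 3 removals among 33 treated subjects leave the all-treated improvement rate uncertain by 3/33, or 9.1 percentage points. A reader might infer that the reported benefit is overstated. That requires every removed subject to be a non-responder, which nothing in the documents establishes. No figure in the plan is shown to be wrong. If the redacted text already provides follow-up after removal, what remains is a missing cross-reference.

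**What to change.** In Section 5.7, take out removal from the study as a consequence of non-compliance and add wording such as:

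*A subject judged non-compliant remains in the study and is asked to attend the remaining scheduled visits, including Visits 6 and 7, for all planned assessments (wrinkle grading, CGAIS, SGAIS, questionnaire, photographs, TEWL, OCT, ultrasound, BTC 2000 and adverse event questioning), unless the subject withdraws consent.*

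Put the same sentence in Section 11. If redacted text already covers follow-up, cross-reference it from both sections. Any decision about treatment is left unchanged.

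Use the added data for adverse event reporting and an all-treated sensitivity analysis beside the per-protocol analysis. The cost is a short amendment, which Section 13 sends to the IRB before implementation, and a few extra attendances at visits already in the schedule.

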6. SUBJECT ENROLLMENT AND INSTRUCTIONS

6.1. Number of Subjects

At least 33 subjects meeting the eligibility requirements are expected to complete participation in the clinical trial.

6.1.1. Determination of Sample Size

The sample size determination of this study [REDACTED]

[REDACTED]

6.2. Informed Consent Form

An IRB-approved informed consent form (ICF), [REDACTED] will be given to each candidate subject before participation in any study procedures. The candidate subject will be given as much time as needed to read the ICF and will have the opportunity to have any study related questions answered to their satisfaction prior to signing the ICF. [REDACTED]

[REDACTED]

[REDACTED]

[REDACTED]

6.3. Subject Identification

Subjects will be assigned a 3-digit number which, [REDACTED] This number will remain with [REDACTED]
[REDACTED]

6.4. Eligibility Criteria

Individuals will be admitted to the study at the discretion of the Investigator or designee, based on medical history and findings of the pre-study interview and examination. Individuals will be screened for the eligibility criteria listed below prior to study enrollment.

6.4.1. Inclusion Criteria

This figure is a complex black and white bar chart. It consists of numerous horizontal bars of varying lengths and positions. The bars are organized into several groups, some of which are aligned vertically. The chart uses a minimalist style with no grid lines or numerical scales. The bars are rendered in black against a white background, with some bars having internal black segments. The overall structure is dense and abstract.

A large number of black horizontal bars of varying lengths, some with small black squares attached, arranged in a grid pattern. The bars are of different lengths and are positioned in a grid-like structure. Some bars have small black squares attached to them.

[REDACTED]

[REDACTED]

[REDACTED]

[REDACTED]

[REDACTED]

[REDACTED]

[REDACTED]

6.5. Subject Instructions

Subjects will be provided with the following instructions to follow during the study:

[REDACTED]

[REDACTED]

- To keep skincare product consistency, Subjects will be offered [REDACTED]
[REDACTED] Sunscreen is recommended to be applied each morning and prior to any sun exposure.

6.5.3. Subject Instructions for Study Visits

- Remove all makeup at least 30 minutes prior to each scheduled clinic visit using the provided facewash. [REDACTED]

6.5.4. General Study Instructions

- Avoid extended periods of sun exposure and all use of tanning beds for the duration of the study. Extra care should be taken to wear protective clothing, including sunglasses, and avoid sun exposure from 10 AM to 4 PM.
- [REDACTED]

[REDACTED]

[REDACTED]

[REDACTED]

[REDACTED]

[REDACTED]

7. STUDY DESIGN

7.1. Description

This is a study to evaluate the efficacy of the microneedling device in improving [REDACTED] Overall assessment of clinical outcome and safety will be based on clinic visits and evaluation of pre- and post- procedural photos. These photos will be [REDACTED] [REDACTED] and subjects will be adequately informed of such. In conjunction with standard and close-up photography, [REDACTED] high-resolution ultrasonography, optical coherence tomography, transepidermal water loss measurements, and/or

BTC 2000 measurements. [REDACTED]

[REDACTED]

[REDACTED]

7.2. Outline of Procedures

	Visit 1	Visit 2	Visit 3	Visit 4	Visit 5	Visit 6	Visit 7
Procedures/Time Points:							
ICF, and qualification/enrollment paperwork							
Urine pregnancy test							
Clinician's Global Aesthetic Improvement Assessment							
Imaging Procedures ^b							
Patient Satisfaction Questionnaires							

7.3.

[REDACTED]

8. CONDUCT OF STUDY

8.1. Pre-Study Procedures

1. Prior to the start of the study, prospective subjects will be screened for eligibility requirements by telephone.
2. Prospective subjects will be informed of the pre-study washout phase pre-visit procedures as described in sections 5.5.1 and 5.5.3.

3. Prospective subjects will be assigned an appointment time for visiting the clinic.

8.2. Baseline: Visit 1 (-14 to 0 day[s])

1. Candidate subjects will be given an IRB-approved informed consent form (ICF)
[REDACTED]
2. Candidate subjects will complete an eligibility and health questionnaire.
3. Candidate subjects that sign the initial paperwork will be assigned a screening number.
4. Candidate subjects will be screened by the Investigator or designee for qualification criteria.
5. Candidate subjects that pass the initial screening will be graded for wrinkle severity and as described in section 8.1.
6. Those that pass eligibility requirements and are female will perform a pregnancy test (if necessary); if the test is negative or the candidate subject is male, the subject will be enrolled into the study and assigned a subject number.

8.3. Interim Visits: Visits 2-5

- A clinician will record concomitant medications and will ask subjects if they have experienced any changes in their health since the previous visit.
[REDACTED]
- [REDACTED]
- 3. After acclimation, subjects will participate in TEWL Measurements, OCT images, high frequency ultrasounds images, BTC images and imaging procedures as described in section [REDACTED]
[REDACTED]
- 5. Trained aestheticians will treat [REDACTED]
[REDACTED]
- 6. Subjects will be provided with supporting materials, usage instructions and a daily diary. New diaries will be distributed at Visit [REDACTED]

8.4. Post-Treatment Visit: Visit 6

- A clinician will record concomitant medications and will ask subjects if they have experienced any changes in their health since the previous visit.
[REDACTED]

2. Supporting products and daily diary distributed at Visit █ will be reviewed for compliance. █
█
█
█
3. After a 15 minute acclimation to ambient temperature and humidity conditions, subjects will participate in the following procedures:
 - Imaging procedures as described in section █
 - Assessment of Wrinkle █
 - Clinician's global aesthetic improvement assessment as described in section █
 - Subject's self-assessment on improvement as described in section █
 - Patient Satisfaction Questionnaire as described in section █
 - TEWL measurement, OCT images, high frequency ultrasound images and BTC 2000 measurement.

8.5. Post-Treatment Visit: Visit 7

1. A clinician will record concomitant medications and will ask subjects if they have experienced any changes in their health since the previous visit. [REDACTED]
2. Subjects will participate in pregnancy screening procedures.
3. After a 15 minute acclimation to ambient temperature and humidity conditions, subjects will participate in the following procedures:
 - Imaging procedures as described in section [REDACTED]
 - Assessment [REDACTED] wrinkle [REDACTED]
 - Clinician's global aesthetic improvement assessment as described in section [REDACTED]
 - Subject's global aesthetic improvement as described in section 8.2.2
 - Patient Satisfaction Questionnaire as described in section 8.6.
 - TEWL measurement, OCT images, high frequency ultrasound images and BTC 2000 measurement.

ASSESSMENTS

Note that the order of the assessment listed below may be altered from the order indicated in the study visits in order to help study flow, or at the recommendations of the Sponsor or Investigator. Any change in the order of procedures will not compromise study data.

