9.3.2. Nikon D7100

Standard, close-up and cross-polarized photography of [REDACTED] neck will be utilized for evaluation of [REDACTED] wrinkles. These photographs will be taken utilizing the Nikon [REDACTED]

[REDACTED]

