9.4. Noninvasive Procedures

Biox Aquaflux will be used to measure transepidermal water loss (TEWL) measurements which evaluate barrier function of the skin epidermal layer to determine progress of epidermal healing after treatment. [REDACTED] an Optical coherence tomography (OCT) device, will be used to noninvasively gather [REDACTED] images of pre- and post-treated skin. The BTC 2000 will be used to measure skin laxity, viscoelastic deformation, stiffness, energy absorption, elasticity, and deformation values of skin. [REDACTED]

[REDACTED]

[REDACTED]

[REDACTED]
[REDACTED]
[REDACTED]
[REDACTED]
[REDACTED]
[REDACTED]

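### The visit lists indicate different orders for photographs and instrument readings before and after treatment, and section 9 lets the order vary further, so pre/post photographs (and to a lesser extent TEWL) are exposed to a possible order effect

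*Combined protocol and SAP*

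**What the plan says.** **Visits 2-5 (protocol 8.3, item 3).** After acclimation, "subjects will participate in TEWL Measurements, OCT images, high frequency ultrasounds images, BTC images and imaging procedures as described in section"; the section number that follows is redacted. This is one running sentence. It names TEWL, OCT, ultrasound and BTC, and then photography. Treatment is item 5, so these readings come before that visit's treatment.

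**Visits 6 and 7 (8.4 and 8.5, item 3).** After a 15-minute acclimation, "subjects will participate in the following procedures". Bullets follow: imaging first, then the wrinkle assessment, the clinician's and the subject's improvement assessments, the satisfaction questionnaire and finally "TEWL measurement, OCT images, high frequency ultrasound images and BTC 2000 measurement".

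**Opening note of section 9.** It says that "the order of the assessment listed below may be altered from the order indicated in the study visits", either to help study flow or because the Sponsor or the Investigator recommends it. It adds that no such change will harm the study data. The visible text gives no reason for that assurance and does not ask for the order used to be recorded.

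**Use of the photographs.** Section 7.1 bases the overall judgement of outcome and safety on clinic visits and on photographs from before and after the procedure. Section 9.3.2 provides for "Standard, close-up and cross-polarized photography of" the neck to evaluate wrinkles. Section 9.3 requires at least 15 minutes of equilibration before any photograph.

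**Analysis.** All subjects receive the device (5.4). Section 15.2 tests mean change from baseline against zero, two-sided at 0.05. At least 33 subjects are expected to complete (6.1).

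**The concern.** A before/after comparison is clean only if both measurements are made under the same conditions. If the lists are followed, the pre-treatment photograph is taken after four instrument readings and the follow-up photograph before them. One of those readings acts mechanically on the skin: section 9.4 says that the "BTC 2000 will be used to measure skin laxity, viscoelastic deformation, stiffness, energy absorption, elasticity, and deformation values of skin". If it, or a probe placed on the skin, left redness or a mark within the photographed field, that would appear in the earlier picture and not in the later ones, and would favour apparent improvement.

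TEWL moves as well. In 8.3 it is the first reading after acclimation. In 8.4 and 8.5 it follows photography, grading and the questionnaire, so the time at rest before it may differ.

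With no concurrent control, any consistent shift of this kind goes straight into the mean change and is read as a device effect.

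**Working it through.** The documents give no figure on procedure order, so there is none to reproduce. The check is a comparison of the lists, followed by an illustration.

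**1. Position of each item within item 3**

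| Item | 8.3 (Visits 2-5) | 8.4 and 8.5 (Visits 6, 7) |
|---|---|---|
| Imaging | last | first |
| Wrinkle assessment | not in the visible list | second |
| Global assessments, questionnaire | not in the visible list | middle |
| TEWL | first | last bullet, first within it |
| OCT, ultrasound, BTC | after TEWL, in that order | after TEWL, in that order |

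The four instruments keep the same order among themselves, so any carry-over from one instrument to the next is the same in all three lists. What changes is the position of the photographs relative to the instruments, and the amount of activity before TEWL.

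**2. Do the lists indicate a sequence?** None of the three says so. The section 9 note nevertheless speaks of an order indicated in the study visits, so the protocol itself reads them that way, though without making the order binding. There are two cases:

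- If the written order is followed, it differs between 8.3 and 8.4/8.5.
- If it is not followed, the order is left to study flow or recommendation and need not be recorded.

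Neither case standardises the comparison.

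**3. Which reading is the pre-treatment one?** The visible text of 8.2 (Visit 1) lists wrinkle grading but no photographs or instrument readings. The first visible mention of them is in 8.3, ahead of treatment. Visit 2 as the photographic baseline is therefore an inference. The schedule in 7.2 has empty cells, and parts of 8.3 and 9.3 are redacted.

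**4. Is the wrinkle grade exposed?** At Visit 1 the grade is made with no instrument reading in the visible text. At Visits 6 and 7 it is listed before the instruments. A live grade therefore precedes the instruments at both ends. A grade read from photographs would not have that protection. The visible text does not say which is used.

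**5. Illustration of sensitivity.** Inputs from the documents: n = 33 (6.1), two-sided alpha = 0.05 (15.2). The test method is redacted, so a one-sample t-test on the change score is assumed, with true change zero. The shift d, in SDs of the change score, is also assumed.

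Noncentrality = d × √33 = d × 5.745; critical value t(0.975, 32 df) = 2.037; rejection probability = P(|T| > 2.037), where T is noncentral t on 32 df.

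| Assumed shift d | Noncentrality | Rejection probability |
|---|---|---|
| 0 | 0 | 5.0% |
| 0.1 | 0.574 | 8.6% |
| 0.2 | 1.149 | 20.0% |
| 0.3 | 1.723 | 38.7% |
| 0.5 | 2.872 | 79.5% |

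For a photograph-based grade in Lemperle classes, assume an SD of change of 0.8, 0.6 or 0.5 class and count only false improvement (nominal 2.5%). A shift of 0.1 class gives d = 0.125, 0.167, 0.2 and rates of 10.3%, 15.1%, 19.9%. A shift of 0.2 class gives d = 0.25, 0.333, 0.4 and rates of 28.5%, 45.9%, 60.6%.

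Every shift and SD here is assumed. The tables show what a consistent shift would do, not that one is present.

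**The case against.** The strongest reply is that this is untidy wording and not a bias.

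- **The order is not binding.** 8.3 is a running sentence, 8.4 and 8.5 are unnumbered bullets under a neutral lead-in, and the section 9 note permits change. The order used at any visit cannot be known from the text. This stands, and it rules out saying that pre-treatment photographs *are* taken on disturbed skin. It does not supply a common order.
- **Redacted text may settle the matter.** Photograph timing or a fixed sequence could sit in the hidden parts of 8.3, 9.3 or 9.4. This stands as a limit. The visible section 9 note still leaves the order open.
- **The mechanism is not documented.** Section 9.4 says what the BTC 2000 measures. It does not say that the device leaves marks, for how long, or whether the probe site lies within the photographed field. The Lemperle classes in 9.1 describe wrinkle depth and edges, not redness. This stands, so both the direction and the size of any effect are open.
- **The listed wrinkle grade largely escapes.** This stands for live grading, as shown in step 4 of the working.
- **TEWL is a minor matter.** It is not named in the visible endpoint list, section 9.4 ties it to epidermal healing, and 8.3 gives no acclimation time, so a longer rest at follow-up is not established. This stands, and TEWL is secondary here.

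The equilibration required in 9.3 does not answer the point. It concerns ambient conditions, and 8.3 places acclimation ahead of the instrument readings.

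A reader might infer from the two lists that the pre/post comparisons carry an order artefact in favour of the device. The documents do not support that: they fix no order, report no effect of the instruments on later photographs, and give no magnitude.

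**Conclusion.** The point holds as an exposure, not as a demonstrated bias. The lists indicate different orders, the section 9 note lets the order vary further, and its assurance of no harm has no visible support. The comparison of photographs, on which 7.1 partly bases the outcome, is therefore open to an order effect that a one-group test of change against zero cannot distinguish from treatment. TEWL is exposed to a lesser degree.

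The size is unknown. The rejection rates rest entirely on assumed shifts and SDs and should not be quoted as error rates of this trial. The conclusion also rests on inferring Visit 2 as the photographic baseline, and it touches the wrinkle endpoint only if grading is done from photographs. Severity is low. It is worth raising because the correction is free and removes an avoidable objection to the before/after evidence.

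**What to change.** 1. In 8.3, 8.4 and 8.5, state one common order and say that it is a sequence: acclimation of the same stated length, photographs and any wrinkle grading, then TEWL, OCT, ultrasound and BTC 2000. This keeps the instruments' existing relative order. The essential element is a common order; photographs come first so that no instrument reading can affect them.
2. Replace the assurance in the opening note of section 9 with a rule that the order is the same at every visit for a given subject, including the pre-treatment visit, and that any departure is recorded with the visit data.
3. If photographs or instrument readings are also taken at Visit 1, apply the same order there.

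The cost is protocol wording through the usual amendment and IRB route, plus one field to record departures. Procedures, staff and visit length stay the same.
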